Cathodal Transcranial Direct  
Current Stimulation (tDCS) in  
Mild Cognitive Impairment  
(MCI): A Randomized, Double-  
Blind, Sham-Controlled Pilot  
Study

NCT# 03521089

July 19, 2017

**Cathodal Transcranial Direct Current Stimulation (tDCS) in Mild Cognitive Impairment (MCI): A Randomized, Double-Blind, Sham-Controlled Pilot Study**

**Principal Investigator:** [name], MSc (Advisor/Primary Mentor)

**PhD Candidate:** [name]

**Co-investigators:** [name], DO, MS; [name]; [name]; [name]; [name]; [name]; [name]; [name], PhD

Title	Cathodal Transcranial Direct Current Stimulation (tDCS) in Mild Cognitive Impairment (MCI): A Randomized, Double-Blind, Sham-Controlled Pilot Study
IRB Protocol Number	16-007478
Phase	Pilot
Study Design	Randomized (1:1), double-blind, sham-controlled
Overall Study Duration	12 months
Participant Participation Duration	8 weeks
Objectives	
 
(1) To compare the effects of cathodal tDCS applied to the right dorsolateral prefrontal cortex (DLPFC) on cognitive outcomes as measured by the NIH Toolbox Cognition Battery 1-month post treatment as compared to baseline in participants with MCI.
 
(2) To compare the effects of cathodal tDCS applied to the right dorsolateral prefrontal cortex (DLPFC) on cognitive outcomes as measured by the NIH Toolbox after 1 session of tDCS in participants who are cognitively unimpaired (CU).
 
(3) To compare the effects of cathodal tDCS applied to the right dorsolateral prefrontal cortex (DLPFC) on cognitive outcomes as measured by the NIH Toolbox after 1 session of tDCS in participants who have MCI.
 

Number of Participants	44 MCI participants in 5 day intervention: 22 in each arm (active vs sham); 44 CU participants in the 1 day intervention: 22 in each arm (active vs sham); 44 MCI participants in the 1 day intervention: 22 in each arm (active vs sham)
Diagnosis and Main Inclusion Criteria	Diagnosis of mild cognitive impairment or cognitively unimpaired healthy elderly (verified by the Montreal Cognitive Assessment), male/female aged 55-85, right handed
Study Device	Soterix Medical 1x1 Low Intensity Transcranial Electric Stimulator (tES) Model 2001: Stimulates cerebral cortex at low intensity (up to 2mA) resulting in changes in cortical excitability and neural plasticity
Duration of Exposure	5 Day MCI: Cathodal stimulation over the right DLPFC (with reference electrode on left DLPFC) will occur at 1.5mA intensity for 15 minutes over 5 consecutive treatment sessions (completed within 1 week) in participants with MCI. Cathodal stimulation over the right DLPFC (with reference electrode on left DLPFC) will occur at 1.5mA intensity for 15 minutes over 1 treatment session in participants who are cognitively unimpaired (CU) or for participants with MCI who are enrolled in the 1 Day intervention.

Statistical Methodology	
Continuous variables will be summarized as a mean <math>\pm</math> SD or median (range). Categorical variables will be summarized using number and percentage. Univariate descriptive statistics and frequency distributions will be calculated as appropriate for all variables. Stratified analysis for age in deciles will also be performed. Comparisons between sham and active tDCS (between group comparisons) will be made by one-way Analysis of Covariance (ANCOVA) method to compare the post-intervention test scores adjusting for baseline (pre-intervention) scores for the NIH Toolbox Cognition Battery (NTCB). Paired t-tests will be used for within group comparisons for NTCB scores. The NIH Toolbox Cognition Battery has six subdomains: Executive Function (NIH Toolbox Flanker Inhibitory Control and Attention Test, NIH Toolbox Dimensional Change Card Sort Test), Attention (NIH Toolbox Flanker Inhibitory Control and Attention Test), Episodic Memory (NIH Toolbox Picture Sequence Memory Test, NIH Toolbox Auditory Verbal Learning Test), Language (NIH Toolbox Picture Vocabulary Test, NIH Toolbox Oral Reading Recognition Test), Processing Speed (NIH Toolbox Pattern Comparison Processing Speed Test, NIH Toolbox Oral Symbol Digit Test), Working Memory (NIH Toolbox List Sorting Working Memory Test). Each subdomain separately, in addition to the NIH Toolbox Cognitive Function Composite Score, will be computed using the Fully Adjusted Scale score adjusted to normative data. Statistical significance will be accepted for two-sided p-values less than 0.05. To control for multiple comparison issues, p-values from pairwise comparisons will be adjusted using the false discovery rate method.

-------------------------	--

**Abstract:**

Mild cognitive impairment (MCI) is an intermediate stage between normal cognition (cognitively unimpaired) and dementia. MCI represents a critical window of opportunity for intervening and potentially altering the trajectory of cognitive decline. In addition, aging is associated with functional decline in a wide range of cognitive domains, and healthy elderly who are cognitively unimpaired (CU) may have pre-symptomatic cognitive impairment (with underlying brain pathology changes occurring). Transcranial direct current stimulation (tDCS), a non-pharmacological method, provides a non-invasive way to electrically stimulate the brain by altering the excitability of cortical areas by its polarizing effects on neuronal resting membrane potentials. The trajectory of connectivity changes over the disease course of MCI and Alzheimer’s disease (AD) is largely unclear. Cross-sectional and longitudinal studies in symptomatic individuals suggest that AD pathology spreads along brain connections, leading to the hypothesis that neurodegenerative diseases might be ‘networkopathies.’ Studies reveal that many older adults who were cognitively unimpaired (CU) and those with MCI perform worse on cognitive tasks and “over-recruit” brain regions that are not activated in younger cohorts performing the same task. However, this paradigm is still controversial and understudied [1]. Some posit that it supplements the functioning of a failing network, while others propose it is potentially detrimental either through general breakdown in the functional specialization of the cortex, or an inability to shut down activity not related to the cognitive task at hand. Cathodal transcranial direct current stimulation (tDCS) is generally considered to be inhibitory, which may be able to modulate neuroplasticity-related functions, suppress maladaptive patterns, and influence learning by network reorganization [2]. We propose to use low intensity (1.5mA) cathodal/sham tDCS on patients with MCI to stimulate (inhibit) the right DLPFC in five consecutive sessions to address the potential maladaptive over activity seen in early cognitive impairment and to measure cognitive outcomes. We will also use the same tDCS montage on participants who are cognitively unimpaired (CU) who will receive 1 treatment session. In addition, there will be another MCI arm that will receive the same treatment as the CU arm for comparison on the 1 treatment session.

**Specific Aims:**

**1) To compare the effects of 1.5mA cathodal tDCS applied for 5 consecutive days to the right DLPFC on cognitive outcomes in participants with MCI as measured by the NIH Toolbox Cognition Battery at 1 month post treatment compared to baseline.**

**1)** We will assess whether 5 consecutive sessions of cathodal tDCS (1.5mA, 15 minute stimulation) applied over the right DLPFC is associated with improved cognitive outcomes after one month. Participants will be randomized 1:1 to active or sham treatment.

**2) To compare the short term effects of 1 session of 1.5mA cathodal tDCS applied to the right DLPFC on cognitive outcomes in healthy elderly who are cognitively unimpaired (CU) and MCI as measured by the NIH Toolbox.**

**2)** We will assess whether 1 session of cathodal tDCS (1.5mA, 15 minute stimulation) applied over the right DLPFC is associated with improved cognitive outcomes after 1 treatment session. Participants will be randomized 1:1 to active or sham treatment. We will have two arms- one CU and one MCI.

**Hypothesis:** Studies indicate that older adults who are cognitively unimpaired who perform worse on cognitive tasks and those with MCI “over-recruit” brain regions that are not activated in younger individuals performing the same task [1]. Here, we hypothesize that inhibition of the right DLPFC counteracts maladaptive recruitment of the bilateral DLPFC, which will affect cognitive outcomes and neurophysiological measurements.

**Background/Significance:** Transcranial direct current stimulation (tDCS) is a non-invasive brain stimulation similar to rTMS. The mechanism of action in tDCS is a subthreshold modulation of neuronal membrane potentials, which alters cortical excitability and activity dependent on the current flow direction of the target neurons [3]. tDCS changes the likelihood of neuron action potential discharge. It involves the application of a weak electrical current (1-2mA) through the scalp. Unlike rTMS, tDCS is not focal or localized through MRI, but relies on the International 10-20 electrode placement system. tDCS has the ability to do sham stimulation and can keep the double-blind on the study through pre-programmed settings. tDCS is for investigational use only and is not currently FDA approved.

The trajectory of connectivity changes over the disease course of healthy aging/cognitively unimpaired participants and those with MCI and AD is largely unclear. Cross-sectional and longitudinal studies in symptomatic individuals suggest that pathology spreads along brain connections, leading to the hypothesis that neurodegenerative diseases might be ‘networkopathies’ [4]. An important study by Guedj et al 2009 investigated the relationship between entorhinal and hippocampal MR volumes and whole-brain SPECT perfusion and connectivity in patients with amnesic MCI with a memory profile suggestive of early AD dementia [5]. They report a strong negative correlation between medial temporal lobe volumes and right dorsolateral prefrontal perfusion at a basal state [5]. This study contrasts the findings of patients with AD where hippocampal atrophy is correlated with a decrease in metabolism in the DLPFC, and suggests that the mechanisms of reorganization, where the right DLPFC may be overactive, affects patients at the stage of MCI [5]. It is unknown whether this relationship, specifically an overactive right DLPFC, compensates for cognitive impairment in an appropriate way or rather, illustrates a maladaptive mechanism related to the lack of normal connectivity. We propose to use cathodal tDCS on patients with MCI and those who are cognitively unimpaired (CU) to stimulate the right DLPFC to address the potential maladaptive over activity seen in early cognitive impairment and measure cognitive outcomes. Other studies have reported enhancement of cognitive function in patients who are CU or have AD or MCI with five or fewer rTMS treatment sessions [6-11]. To our knowledge, the only study employing tDCS in MCI patients employed a single-session protocol, but numerous AD tDCS studies also support enhancement with five or fewer session [12-15]. The importance and clinical relevance of this project is to expand the use of non-invasive brain stimulation (tDCS) in Arizona, with the hopes of translating this into clinical practice. The results of this project will improve AZ practice of medicine and advance the body of scientific knowledge in the field of MCI. This project will be the first in AZ to utilize the Soterix tES device, which serves as important leverage to establish project feasibility and to increase awareness and visibility of this technology at MCA and its availability to all investigators in all departments. The advantages of tDCS include portability (can be used anywhere in MCA), inherent NSR determination, and ease of use for interested investigators.

**Experimental Approach:**

**Accrual plan:** Participants will be identified through medical records, a flyer posted internally at Mayo Clinic Scottsdale and Phoenix, and by referrals from other Mayo physicians. The HABIT program led by [name] is very visible in the MCI community, and there exists a database of past MCI participants who may be interested in joining. Approval from the Mayo Clinic Institutional Review Board is necessary and all participants will provide written informed consent prior to participation in this study.

**Power and Sample Size Calculation:** A systematic review and meta-analysis examining effects of tDCS on cognitive function in AD shows an estimate effect size of 0.76 on outcomes similar to that of the NIH Toolbox Cognition Battery [16]; for our pilot study, a conservative estimate effect size ( $d=0.60$ ) was used due to time of

intervention. A calculated sample size of 38 (19 for each group) was derived from an ANCOVA method adjusting for pre-intervention scores with an alpha of 0.05 error, which will have 70% power to reject the null hypothesis. Thus, 38 participants (19 in each arm) will provide sufficient power. For the 5 day intervention, **we aim to enroll 44 participants with MCI total (22 in each arm), with an anticipated drop out or loss-to-follow up accounted for 10-15% in the statistical analysis to realistically achieve 19 participants per group.** For the 1 day intervention, both the cognitively unimpaired group and MCI group will be identical: we aim to enroll 44 CU participants (22 in each arm) and 44 MCI participants (22 in each arm), with an anticipated drop out or loss-to-follow up accounted for 10-15% in the statistical analysis to realistically achieve 19 participants per group.

**Sex/minority mix:** Although studies have found a higher incidence and prevalence of MCI in men, this study will strive to include 50% women [17, 18]. No discrimination or exclusion of female or minority participants will occur. Adherence to the inclusion and exclusion criteria of the study will be free of bias from race, gender, culture or religious background.

**Inclusion Criteria:**

- Male or female outpatients with confirmed MCI diagnosis or who are cognitively unimpaired (CU) as verified by the Montreal Cognitive Assessment (MoCA) scoring  $\geq 26$ .
- Age 55-85
- Right handed (tested using the Edinburgh handedness inventory [19])
- Total PHQ-8 of  $\leq 9$  which signifies no moderate or severe depression [20]
- All participants and/or caregivers must be able to provide informed consent

**Exclusion Criteria:**

- Neurodegenerative disease (e.g. Parkinson's, Huntington's, Multiple Sclerosis) other than MCI
- Previous brain lesion
- Intracranial abnormality such as prior stroke
- History of seizure disorder or epilepsy
- A "true" positive response, after patient clarification, to any question on the modified TMS/tDCS Adult Safety Screen questionnaire that would impact patient safety [21] (Refer to **Appendix A**)
- Any history of brain stimulation treatment (e.g., electroconvulsive therapy (ECT), repetitive transcranial magnetic stimulation (rTMS), vagal nerve therapy (VNS), deep brain stimulation (DBS))
- Use of any investigational drug within 4 weeks
- Cardiac pacemakers, implanted medication pumps, intracardiac lines; acute or unstable cardiac disease; intracranial implants (e.g., aneurysm clips, shunts, stimulators, cochlear implants, or electrodes) or any other metal object within or near the head (exception: mouth/dental work) that cannot be safely removed
- Known or suspected pregnancy (extremely unlikely as the age range for this study is 55-85 years)

**Intervention** (independent variable): 5 Day intervention (MCI): Five consecutive weekday tDCS sessions with the Soterix tES system; 1 Day intervention (CU and MCI): 1 tDCS session. Each tDCS session will include cathode electrode placement over the right DLPFC (using the International 10-20 system) at 1.5mA intensity for 15 minutes with anode reference electrode placement over the left DLPFC. The CogState Brief Battery (One Card Learning and One Back Test) is a computerized cognitive battery that will be administered while participants undergo either active or sham tDCS stimulation. Patients who meet the inclusion criteria for the study will be randomized in a 1:1 fashion between sham and active TMS treatment. For this study, we will stratify age in deciles (55-65 years, 66-75 years, 76-85 years), as age is the number one risk factor for neurodegenerative disease. Following randomization, the patients and investigator will be blinded to the treatment group assignment and staff administering treatment will be unblinded. Refer to **Appendix B** for more information regarding device description.

Study Schedule: 5-Day MCI	Pre-Intervention		5 Day Intervention					Follow-Up
	Estimated Time	Screening & Baseline	Day 1	Day 2	Day 3	Day 4	Day 5	1 Month Follow up
Informed Consent	1 hour	x						
Eligibility Checklist 	10 minutes	x						
Adverse Event Monitoring	5 minutes		x	x	x	x	x	
NIH Toolbox: Cognitive Battery 	30 minutes	x					x 	x
CogState Brief Battery  (Simultaneous with intervention)	15 minutes		x	x	x	x	x	
Intervention: 1.5mA tDCS	15 minutes		x	x	x	x	x	

1. Eligibility checklist includes review of inclusion/exclusion criteria, the modified TMS/tDCS Adult Safety Screen questionnaire, Edinburgh handedness inventory, and PHQ-8 questionnaire

2. NIH Toolbox Cognitive Battery includes: NIH Toolbox Picture Vocabulary Test, Flanker Inhibitory Control and Attention Test, List Sorting Working Memory Test, Dimensional Card Sort Test, Pattern Comparison Processing Speed Test, Picture Sequence Memory Test, Oral Reading Recognition Test

3. NIH Toolbox: Cognitive Battery will be administered 5 minutes after stimulation on Day 5

4. CogState Brief Battery will be administered while active or sham stimulation occurs

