**The study will be performed over 7 sessions for MCI participants in the 5 Day Intervention (Figure 1):**

- **Visit 1 (Screening and Baseline visit):** This will occur ~1-2 weeks before the Five Day Intervention. The purpose of this visit is to obtain informed consent for the study, to screen participants for inclusion and exclusion criteria, and obtain baseline performance of the participant's NIH Toolbox Cognition Battery and CogState Brief Battery (One Card Learning and One Back Test). The TMS/tDCS Adult Safety Screen questionnaire, Edinburgh handedness assessment, and the PHQ-8 will also be administered.
- **Visits 2-6 (Five Day Intervention Days 1-5):** During these visits the participant will receive either active tDCS or sham stimulation. The CogState Brief Battery (One Card Learning and One Back Test) will be administered during stimulation. The visits will take place during a 1-week period (Day 1-5 corresponds to visits 2-6), as five consecutive visits (Monday-Friday). An Adverse Event questionnaire will be administered after each visit. On Visit 5 (last day of intervention), all participants will complete the NIH Toolbox Cognition Battery testing after stimulation.
- **Visit 7 (One month after completion of intervention) follow up visit:** Participants will undergo final NIH Toolbox Cognition Battery. A questionnaire for blind assessment will also be completed.

Study Schedule: 1-Day MCI and CU	Estimated Time	Pre-Intervention	Intervention	Post-Intervention
Informed Consent	1 hour	x		
Eligibility Checklist 	10 minutes	x		
Adverse Event Monitoring	5 minutes		x	
NIH Toolbox: Cognitive Battery 	30 minutes	x		x 
CogState Brief Battery  (Simultaneous with intervention)	15 minutes		x	
Intervention: 1.5mA tDCS	15 minutes		x	

1. Eligibility checklist includes review of inclusion/exclusion criteria, the Montreal Cognitive Assessment (MoCA) >26 (for CU group only), the modified TMS/tDCS Adult Safety Screen questionnaire, Edinburgh handedness inventory, and PHQ-8 questionnaire

2. NIH Toolbox Cognitive Battery includes: NIH Toolbox Picture Vocabulary Test, Flanker Inhibitory Control and Attention Test, List Sorting Working Memory Test, Dimensional Card Sort Test, Pattern Comparison Processing Speed Test, Picture Sequence Memory Test, Oral Reading Recognition Test

3. NIH Toolbox: Cognitive Battery will be administered 5 minutes after stimulation

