4. CogState Brief Battery will be administered while active or sham stimulation occurs

For participants in the 1 day session (MCI and CU) (Figure 2), one visit will include a screening/baseline assessment to screen participants who inclusion and exclusion criteria, and to obtain baseline performance with the NIH Toolbox. The TMS/tDCS Adult Safety Screen questionnaire, Edinburgh handedness assessment, and the PHQ-8 will also be administered, as well as the Montreal Cognitive Assessment (MoCA) >26 for CU participants. Following that, a 15 minute tDCS treatment (active or sham) will be administered and after a rest break, the same assessment using the NIH Toolbox will be repeated. During the tDCS treatment, the participant will do the CogState Brief Battery (One Card Learning and One Back Test). An adverse event questionnaire will be administered after the stimulation.

Risks and Adverse Events: For a full list of risks, see **Appendix C** for more information on anticipated risks. A symptom-based questionnaire will be used to measure adverse events and will be administered at each visit after the screening visit. The frequency and percentage of adverse events will be compared between the 2 treatment arms. Comparisons between arms will be made by using either the Chi-square or the Fisher's exact test.

Safety Evaluation: A literature review showed that all tDCS trials between 1998-2010 [22] showed that of the 209 studies, similar rates in frequency of adverse events in the active vs. sham arms were observed. The most common AE were headache, itching, burning, discomfort and tingling, occurring in 10-40% of patients regardless of treatment group. Refer to **Appendix D** for the Data and Safety Monitoring Plan.

Efficacy Evaluation: The primary outcome measurement is the NIH Toolbox Cognition Battery either at 1 month after intervention (MCI) or after 1 tDCS session (CU and MCI) as compared to baseline scores.

Expected outcomes: We anticipate a change in the NIH Toolbox Cognition Battery scores in the 1-month follow up scores (MCI) or after 1 tDCS session (CU and MCI) as compared to baseline and do not anticipate any change in the sham group.

Statistical analysis: Continuous variables will be summarized as a mean  $\pm$  SD or median. Categorical variables will be summarized using number and percentage. Univariate descriptive statistics and frequency distributions

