will be calculated as appropriate for all variables. Stratified analysis for age in deciles and sex will also be performed. Comparisons between sham and active tDCS (between group comparisons) will be made by one-way Analysis of Covariance (ANCOVA) method to compare the post-intervention test scores between active tDCS group and sham group and adjusting for their baseline (pre-intervention) scores for the NIH Toolbox Cognition Battery. Paired t-tests will be used for within groups for ADAS-cog scores. For analysis of the NIH Cognition Battery, the same method (ANCOVA, paired t-test) will be used. NIH Toolbox Cognition Battery has six subdomains: Executive Function (NIH Toolbox Flanker Inhibitory Control and Attention Test, NIH Toolbox Dimensional Change Card Sort Test), Attention (NIH Toolbox Flanker Inhibitory Control and Attention Test), Episodic Memory (NIH Toolbox Picture Sequence Memory Test, NIH Toolbox Auditory Verbal Learning test), Language (NIH Toolbox Picture Vocabulary Test, NIH Toolbox Oral Reading Recognition Test), Processing Speed (NIH Toolbox Pattern Comparison Processing Speed Test, NIH Toolbox Oral Symbol Digit Test), Working Memory (NIH Toolbox List Sorting Working Memory Test). Each subdomain separately, in addition to the NIH Toolbox Cognitive Function Composite Score, will be computed using the Fully Adjusted Scale score adjusted to normative data. CogState Brief Battery (One Card Learning and One Back Test) will not be included in statistical analysis. Statistical significance will be accepted for two-sided p-values less than 0.05. To control for multiple comparison issues, pairwise comparisons p-values between the groups will be adjusted using the false discovery rate method.

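### The role of the 5-day cohort's Day 5 NIH Toolbox score is not stated, and the planned one-outcome ANCOVA omits anyone without a 1-month score even when a Day 5 score is on file

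*Combined protocol and SAP*

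**What the plan says.** The table Study Schedule: 5-Day MCI puts the NIH Toolbox at baseline, Day 5 and 1 month. Its footnote 3 reads "NIH Toolbox: Cognitive Battery will be administered 5 minutes after stimulation on Day 5". The visit description says of the same test: "On Visit 5 (last day of intervention), all participants will complete the NIH Toolbox Cognition Battery testing after stimulation".

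Aim 1 defines the outcome "as measured by the NIH Toolbox Cognition Battery at 1 month post treatment compared to baseline". The Efficacy Evaluation paragraph likewise gives 1 month as the primary time for this cohort.

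The Statistical analysis paragraph, like the Statistical Methodology row of the synopsis, plans a one-way ANCOVA to "compare the post-intervention test scores between active tDCS group and sham group and adjusting for their baseline (pre-intervention) scores", plus within-group paired t-tests. Neither names a visit, a repeated-measures model, an analysis population or a rule for missing scores. The only test expressly set aside is CogState: "CogState Brief Battery (One Card Learning and One Back Test) will not be included in statistical analysis".

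Attrition appears only under Power and Sample Size Calculation, which has "loss-to-follow up accounted for 10-15% in the statistical analysis" and expects 22 enrolled per arm to become 19.

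**The concern.** The cohort has two post-intervention scores and the analysis takes one outcome per person. Read with the primary outcome, that outcome is the 1-month score. Someone who completes treatment week, takes the battery on Day 5 and then misses the 1-month visit contributes nothing to the primary comparison, although the Day 5 score says a good deal about the missing one.

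Three things are at stake:

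- **Bias**, if loss depends on Day 5 performance differently in the two arms.
- **A little precision**, even if loss is random.
- **Selective reporting.** With no stated role for Day 5, the choice to report it, and whether it counts in the false-discovery-rate adjustment, can be made after the data are seen.

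Only the 5-day cohort is affected, since the 1-day cohorts have a single post-stimulation score.

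**Working it through.** **The plan's own figures.** Evaluable 38, loss 10-15%: 38/0.90 = 42.2, so 43; 38/0.85 = 44.7, so 45. The plan enrols 44, which agrees. Going from 44 to 38 is 6/44 = 13.6%, or 3 per arm. The 70% power at d = 0.60, two-sided 0.05, 19 per arm depends on a baseline correlation r that is not printed. It is reproduced at r = 0.69: 0.60/√(1−0.69²) = 0.829, times √(19/2) gives a noncentrality of 2.555, and power is 70.0% on 35 df. I use that as the anchor for power.

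**Assumptions, not in the documents.** Correlation r of each later score with baseline, 0.5-0.7. Correlation ρ between Day 5 and 1 month, 0.7-0.85. Three of 22 lost per arm, all with a Day 5 score.

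**Bias, one-sided selection.** Suppose the active arm loses its three lowest Day 5 scorers and the sham arm loses three at random. The three lowest of 22 standard normal values average −1.91, −1.46 and −1.19, summing to −4.56, so the Day 5 mean of the remaining 19 rises by 4.56/19 = 0.24 SD. Their 1-month mean rises by 0.24ρ and their baseline mean by 0.24r. Adjusting for baseline with slope about r leaves

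bias ≈ 0.24(ρ − r²), in favour of active.

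**Precision, random loss.** The Day 5 to 1-month correlation given baseline is p = (ρ − r²)/(1 − r²). A likelihood model using Day 5 then has

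effective n per arm = 1/[(1 − p²)/19 + p²/22].

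| r | ρ | p | bias (SD), one-sided selection | effective n, random loss | ratio to 19 |
|---|---|---|---|---|---|
| 0.5 | 0.70 | 0.60 | 0.11 | 19.98 | 1.05 |
| 0.5 | 0.85 | 0.80 | 0.14 | 20.82 | 1.10 |
| 0.7 | 0.70 | 0.41 | 0.05 | 19.45 | 1.02 |
| 0.7 | 0.85 | 0.71 | 0.09 | 20.39 | 1.07 |

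**Simulation at the same settings**, 3000 trials each. The comparison is the complete-case ANCOVA against a likelihood estimate that fits Day 5 on baseline and arm in everyone, and 1 month on Day 5, baseline and arm in completers.

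- Three lowest lost in active, random in sham: complete-case bias about 0.05-0.15 SD, which is 8-25% of 0.60 (0.05/0.60 and 0.15/0.60).
- Graded selection in active (dropout weight exp(−Day 5 score)), random in sham: 0.02-0.08 SD.
- Three lowest lost in both arms, or random loss in both: within 0.01 SD.
- The likelihood estimate stays within 0.01 SD in all of these. The standard error of the ANCOVA estimate is 0.23-0.29 SD.

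**Power**, random loss, r = 0.69, starting from 70.0%. If all those lost have Day 5 scores, power is 70.5%, 71.5%, 73.0% and 73.9% for p = 0.3, 0.5, 0.7 and 0.8. If half have them, it is 70.3% to 72.1%. If none do, it stays at 70.0%. The ceiling with no loss at all is 76.6%.

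**The case against.** A baseline-adjusted ANCOVA at one primary time point is a standard and valid choice for a pilot, and enrolment is already inflated for the loss. Both points stand. The expected gain under random loss is small, and the ANCOVA is not wrong in itself.

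Three stronger readings are tempting and should not be drawn.

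- **That Day 5 has no role in the analysis.** No sentence says so. The ANCOVA wording names no visit, Day 5 is a post-intervention score, and only CogState is excluded by name, so a separate Day 5 ANCOVA fits the text. The supportable statement is that its role is not given. A separate Day 5 ANCOVA would still leave those without a 1-month score out of the primary comparison.
- **That most or all of the 10-15% falls after Day 5.** The plan gives one figure for drop-out and loss to follow-up together, without timing. The schedule has 1-2 weeks between baseline and Day 1 and then five daily visits. Anyone lost before the Day 5 test has no Day 5 score to use.
- **That the estimate is biased whenever loss relates to Day 5 performance.** With equal numbers lost, the dependence must differ by arm. Participants are blinded, and the multi-session review cited in Appendix C found no higher dropout on active stimulation. That speaks to rates and not to who leaves, but nothing in the documents points to one-sided selection. Even the extreme case is only about half a standard error (0.15/0.28).

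The visit label is a clerical matter. The description maps Days 1-5 to Visits 2-6 and then calls the last day Visit 5, but it and footnote 3 both tie the test to the last intervention day, so the timing is not in doubt.

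**Conclusion.** The point holds as a gap with a cheap improvement, not as a flaw that invalidates the primary analysis. Two post-intervention scores are collected, only one has a stated use, and the stated method cannot use a participant who lacks it. The bias is about 0.05-0.15 SD in a deliberately unfavourable case confined to the active arm, 0.02-0.08 SD under graded selection there, and about 0 if loss is random or the same in both arms. Under random loss the gain is about 2-10% in variance, or roughly 0.5-4 power points. If only one of the three lost per arm has a Day 5 score, the variance gain falls to 1-4%. All of this rests on the assumed correlations and on 3 of 22 lost per arm; the share of those lost who would have a Day 5 score cannot be known from the documents.

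**What to change.** For the 5-day cohort, analyse the Day 5 and 1-month scores in one repeated-measures model with arm, visit, arm-by-visit, baseline score, baseline-by-visit and age stratum, and an unstructured covariance. Include all randomised participants with any post-baseline score. The baseline-by-visit term lets the baseline slope differ by visit, as it does in the estimate checked above.

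Keep the 1-month active-minus-sham contrast as primary, name Day 5 as secondary, and state whether the Day 5 tests enter the false-discovery-rate family.

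The cost is a few sentences in the statistical section and a slightly more complex model, with no new data. The drawbacks are that the gain in precision is modest and that the model relies on loss being explained by the observed scores.

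As a separate editorial point, reconcile the Visit 5 label for the last intervention day with the mapping of Days 1-5 to Visits 2-6 in the same paragraph.
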